4.6 Enrollment and Screen Failures

Subjects who sign an informed consent form (ICF) but are ultimately not enrolled in the trial will be considered screen failures. Subjects will be assigned a subject identification number at the time the ICF is signed. A subject will be considered enrolled once injected with technetium Tc 99m on Day 1. Demographic data and the reason for the screen failure will be collected for all screen failure subjects. Enrollment will continue until a total of up to 14 subjects have completed planar imaging.

Subject Identification

After the subject provides written informed consent, the site will assign the subject a 7-digit subject number. Subject numbers are to be assigned in a sequential manner using the following format:

- Digits 1 to 2: Trial number 24
- Digits 3 to 4: Site number (e.g., "01")
- Digits 5 to 7: Sequential subject number (e.g., "001", "002", "003")

For example, the first subject consented at site 01 is subject number “24-01-001.”

Subjects will maintain the same number given at screening for the entire trial. If a subject is a screen failure, the number will not be used for any other subject.

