 - Follow-up assessment from SC injection including changes in concomitant medication and adverse events
 - Urine pregnancy test will be performed for subjects of child bearing potential within 48 hours of injection
 - Concomitant medication review
 - Vital signs—within 30 minutes prior to injection

Tc 99m Tilmanocept IV Injection: Subjects will receive their open label serial IV dose assignment in accordance with Table 1. Adverse event monitoring will continue through completion of the trial.

Post-Tc 99m Tilmanocept Injection:

- Within 30 Minutes Post-Injection
 - ECG
 - Vital Signs
 - Assessment of Adverse Events
- 60-75 Minutes Post -Injection
 - Assessment of Adverse Events
 - Whole body planar imaging followed by optional SPECT/CT scan of region(s) of interest
- At Completion of Imaging:

	
○ Safety Labs○ Biopsy of designated non-visceral KS lesion 
7 ± 3 Days Post-IV Injection Telephone Follow-up:
 
• Assessment of Adverse Events• Concomitant medication review 
For determination of the secondary endpoints, the Tc 99m tilmanocept whole body planar and SPECT/CT images will be visually assessed for localization by a Nuclear Medicine Physician.
	
Planned Study Dates	Start of study recruitment January 2018	End of Recruitment: June 2019 End of Study/ September 2019
Planned number of study centers	One (1) in the United States	
Number of subjects	Total: Up to 14 evaluable subjects may be enrolled, injected, and imaged. KS symptoms will be divided into three categories: a) confirmed cutaneous/oral lesions without edema, b) confirmed cutaneous/oral lesions with edema, or c) confirmed cutaneous/oral lesions with or without edema and suspected non-cutaneous KS due to clinical symptomology or confirmed non-cutaneous lesions. After the subjects are dosed and imaged in each cohort, safety and imaging data will be reviewed by the Co-PIs and Navidea for assessment of safety and preliminary localization.	
Primary Endpoint	Proportion of subjects experiencing noxious pharmacologic activity/Adverse Drug Reaction (ADR).	

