4 STUDY POPULATION

The evaluation of Tc 99m tilmanocept in KS will involve up to 14 enrolled, injected, and imaged subjects.

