4.4 Recruitment

Up to fourteen (14) evaluable subjects will be recruited from medical practice in accordance with the inclusion and exclusion criteria listed above. Potentially suitable subjects will be asked by the treating specialist about their willingness to participate in this trial. An assessment of safety and preliminary localization results will occur at the completion of each cohort. Up to fourteen (14) subjects will be enrolled, injected, and imaged.

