8 PROCEDURES AND VARIABLES

8.1 Population Characteristics

8.1.1 Demographic and Other Baseline Characteristics

Up to fourteen (14) HIV-positive female or male subjects \geq 18 years that have been diagnosed with biopsy-confirmed KS will be enrolled, injected, and imaged. There are no minimum or maximum numbers for gender in the cohorts.

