1.0 Synopsis of Study Design Procedures

This study will enroll up to fourteen (14) HIV (human immunodeficiency virus) - positive female or male subjects at least 18 years of age who have biopsy-confirmed Kaposi Sarcoma (KS).

The primary objective of this study is:

- To determine the safety of escalating doses of Tc 99m tilmanocept in HIV subjects with biopsy-confirmed KS

The secondary objectives of this study are:

- Concordance between clinical assessment/diagnosis and the localization of Tc 99m tilmanocept by planar and/or SPECT (single photon emission computed tomography) / CT (X-ray computed tomography) imaging in cutaneous and non-cutaneous sites of KS.
- Qualify and quantify Tc 99m tilmanocept localization intensity on imaging with CD206 locale and quantity by histology and immunohistochemistry (IHC) in biopsied KS lesions to determine optimal IV dose.
- Concordance of localization of Tc 99m tilmanocept via IV and SC routes of administration by planar and/or SPECT/CT imaging in cutaneous and non-cutaneous sites of KS.

The exploratory objective of this study is:

- Quantify HHV8 in biopsied KS lesions by real-time polymerase chain reaction (qPCR)

General safety will be evaluated by examining the incidence of adverse events (AEs) and changes over time in laboratory tests, vital signs, ECGs (electrocardiogram) and physical examination findings.

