1.3 Sample Size

The dose escalation portion of this study is a design with no dose de-escalation. The sequential cohort enrollment characteristics of this design do not allow a fixed computation of sample size. In a previous study with subjects receiving a 400 µg dose radiolabeled at 10 mCi (i.e., twice the maximum dose planned for this study), zero (0) subjects had an Adverse Drug Reaction (ADR). Therefore, it is expected that no subjects will have an ADR in this study and that each cohort will enroll the minimum planned sample size of subjects. With 2 cohorts of 4 subjects and one cohort of up to 6 subjects, it is anticipated that the study will enroll no more than n=14 subjects.

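### The limit of 14 subjects makes no allowance for expanding both Cohort 1 and Cohort 2 under the 4+2 rule, which would leave Cohort 3 with 2 places

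*Protocol*

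**What the plan says.** The limit appears in five protocol places and in the SAP synopsis, each time without a condition:

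- Protocol synopsis, Number of subjects: "Total: Up to 14 evaluable subjects may be enrolled, injected, and imaged".
- Protocol 4: "The evaluation of Tc 99m tilmanocept in KS will involve up to 14 enrolled, injected, and imaged subjects".
- Protocol 4.4: "Up to fourteen (14) subjects will be enrolled, injected, and imaged".
- Protocol 4.6, as the stopping point for enrolment: "Enrollment will continue until a total of up to 14 subjects have completed planar imaging".
- Protocol 8.1.1: "Up to fourteen (14) HIV-positive female or male subjects".
- SAP 1.0: "This study will enroll up to fourteen (14) HIV".

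Protocol 9.4 and SAP 1.3 show where 14 comes from. Both expect no ADR and add two cohorts of 4 and one of up to 6. The SAP reasons that "each cohort will enroll the minimum planned sample size of subjects" and concludes that "it is anticipated that the study will enroll no more than n=14 subjects".

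Protocol 5.3 gives the escalation rule. One ADR among the four Cohort 1 subjects adds two subjects at that dose, and escalation goes on if neither has an ADR. Section 9 describes the escalation as 4+2 without de-escalation. Table 1 in Section 5.2 sets Cohorts 1 and 2 at 4 and Cohort 3 at up to 6.

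**The concern.** A figure built on the expectation of no ADR is used as an upper limit in a design that adds subjects when ADRs occur. The SAP wording shows this most plainly, moving from minimum cohort sizes to a maximum total. If the earlier cohorts use places for expansion, those places come out of Cohort 3. That cohort carries the 200 µg mass dose and is the only one given both routes, so it alone supports the IV versus SC concordance analysis and its McNemar test.

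In that situation the site could not follow both instructions. Keeping to 14 would leave Cohort 3 too small for a rule that starts from four. Following the rule would exceed the stated maximum, and Section 3.3 requires a formal amendment for any non-administrative change.

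**Working it through.** **The plan's figure.** 4 + 4 + 6 = 14, as in Protocol 9.4 and SAP 1.3. The sum is correct.

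**Places left for Cohort 3 under a limit of 14** (each expansion adds 2):

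- No earlier expansion: 14 − (4 + 4) = 6.
- One: 14 − (6 + 4) = 4. Cohort 3 can run with 4, which its up-to-6 size allows, but cannot add 2.
- Two: 14 − (6 + 6) = 2, fewer than the four the rule starts from.

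**Maximum under the rule.** 6 + 6 + 6 = 18 if Cohort 3's up to 6 already includes any +2. It is 6 + 6 + 8 = 20 if Cohort 3 starts at 6 and can still add 2.

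**Does expansion apply beyond Cohort 1?** Section 5.3 words the trigger for Cohort 1 only. It also provides that, after more than one further ADR in an expanded cohort, the preceding dose level becomes the MTD. Cohort 1 has no preceding level, and the same section says the MTD cannot be determined there with 2 of 4 or 3 of 6 ADRs. That provision, with the 4+2 description in Section 9, makes sense only if a later cohort can be expanded.

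**How likely is a conflict?** The documents expect zero ADRs and give no other planning rate, so the rate p is assumed, equal across cohorts and independent between subjects. The range is 1% to 20%. Section 1.3.4 reports no drug-related reaction in 60 IV subjects, for which the one-sided 95% upper bound is 1 − 0.05^(1/60) = 0.049, about 5%. The value 1% lies nearer the observed zero; 10% and 20% are sensitivity values below the 33% tolerated in the MTD definition.

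Per cohort:

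- Continue without expansion: s = (1 − p)^4
- Expand, then continue: e = 4p(1 − p)^3 × (1 − p)^2 = 4p(1 − p)^5

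Conflict paths:

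- A. Both Cohorts 1 and 2 expand and escalation continues: e²
- B. One of them expands, then exactly one ADR occurs among the first four in Cohort 3: 2se × 4p(1 − p)^3. This counts only if the +2 rule applies in Cohort 3.

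At p = 5%: s = 0.8145 and e = 0.1548. A = 0.1548² = 0.0239 after rounding from unrounded values. B = 2 × 0.8145 × 0.1548 × 0.1715 = 0.0432. The sum is 0.0672.

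| Assumed ADR rate | A: both expand | B: one expands, then one ADR in Cohort 3 | A + B |
|---|---|---|---|
| 1% | 0.1% | 0.3% | 0.4% |
| 5% | 2.4% | 4.3% | 6.7% |
| 10% | 5.6% | 9.0% | 14.6% |
| 20% | 6.9% | 8.8% | 15.7% |

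A simulation of 1,000,000 trials per rate gave totals of 0.43%, 6.72%, 14.66% and 15.69%.

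**The case against.** The strongest reply is that Section 5.3 states the trigger for Cohort 1 alone. On that wording only one expansion is possible, 6 + 4 + 4 = 14 fits, and nothing conflicts. The diagram in Appendix 3 might settle the matter, but it is not visible, and its absence from the text is not a fault of the plan. This stands as a limit on certainty. It does not account for the MTD provision about a preceding dose or for the 4+2 description.

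Second, Section 5.3 can be read as ending escalation when Cohort 3 is reached with a single ADR, so that no +2 is needed there. This also stands. It removes path B and leaves only the double expansion.

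Third, Protocol 9.4 and SAP 1.3 say that the sequential design does not permit a fixed sample size and call 14 anticipated. That helps in those two sections but does not qualify the enrolment stop in Section 4.6 or the other unconditional statements.

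Fourth, the synopsis requires a safety review after each cohort. A double expansion would therefore be known before Cohort 3 opens, leaving time to amend. That lowers the stakes.

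A reader might infer more than the documents support:

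- *Any single expansion breaks the limit.* This requires Cohort 3 to be filled to 6; Table 1 says up to 6.
- *14 is strictly the zero-ADR total.* That holds only if Cohort 3 is filled to 6 at the outset. If it starts at 4, the zero-ADR total is 4 + 4 + 4 = 12, and 14 already covers one expansion.
- *The MTD cannot be determined.* The criterion of no more than 33% can be applied to four subjects.

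**Conclusion.** The limit of 14 is stated without condition but makes no allowance for expansions in both Cohorts 1 and 2. One earlier expansion fits. Two leave 2 places for Cohort 3, with a chance of about 0.1% to 6.9% over assumed ADR rates of 1% to 20%. The wider figures, 0.4% to 15.7%, apply only if the +2 rule also governs Cohort 3.

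The conclusion rests on the inference that Cohort 2 can be expanded, and the probabilities rest on the assumed rates. If the ADR rate is close to the expected zero, the problem is very unlikely to arise. This is a low-priority inconsistency between the stated maximum and the escalation rule. The sum 4 + 4 + 6 is correct, and no power calculation is affected.

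**What to change.** In the protocol synopsis, Sections 4, 4.4, 4.6, 8.1.1 and 9.4, and SAP 1.0 and 1.3, give 14 as the anticipated total if neither Cohort 1 nor Cohort 2 is expanded. Say that subjects added under Section 5.3 are additional, and give a maximum of 18: 6 per cohort, with Cohort 3's up to 6 including any +2. The sponsor should confirm this against the escalation diagram, because the maximum would be 20 if Cohort 3 starts at 6 and can still add 2. Replace the upper limit in SAP 1.3 to match. Section 5.3 should also say whether the trigger applies in Cohorts 2 and 3.

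The cost is a wording change. With a maximum of 18, at most 18 − 14 = 4 further subjects would be enrolled, and none if no ADR occurs.

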5 INVESTIGATIONAL PRODUCT

5.1 Identification of Investigational Product

Tc 99m tilmanocept is a radiopharmaceutical that accumulates in KS lesions and lymphatic tissue by binding to mannose binding receptors (CD206) that reside on the surfaces of dendritic cells and macrophages.

5.2 Investigational Product Dosage and Administration

This study includes IV administration of 3 doses Tc 99m tilmanocept: 100 μ g/ 5 mCi, 100 μ g/ 10 mCi, and 200 μ g/ 5 mCi. All subjects will receive IV administration at one of these three doses. Cohort 3 will serve as a comparator arm, and Cohort 3 subjects will additionally receive a SC injection of Tc 99m tilmanocept at the Cohort 3 dose of 200 μ g/ 5 mCi (see Table 1). At least one subject enrolled into each cohort must meet inclusion criteria 4c (suspected non-cutaneous or confirmed non-cutaneous KS), as described in [Section 4.1](#).

Table 1. Dosing Cohorts

	Tc 99m tilmanocept Dose	Route of Administration	Number of Subjects
Cohort 1	100 μ g/ 5 mCi	IV	n = 4
Cohort 2	100 μ g/ 10 mCi	IV	n = 4
Cohort 3	200 μ g/ 5 mCi	IV and SC	n = up to 6

All subjects will receive Tc 99m tilmanocept through an IV route of administration. A single syringe will be used and injected as a slow push into the venous catheter. The preferred site of catheter placement will be the left or right antecubital vein. Injection volume will be 1.0 mL in sterile normal saline. At the completion of the injection, a 10 cc sterile normal saline flush will be administered.

Cohort 3 subjects will also receive Tc 99m tilmanocept through a SC route of administration. Two syringes will be used and injected bilaterally as a slow push into the ankle(s) or the dorsal surface of the foot (feet). Total injection volume will be 1.0 mL (0.5 in each syringe) in sterile normal saline. Each syringe will contain half of the intended total dose of 200 μ g/ 5 mCi (100 μ g/ 2.5 mCi per syringe).

5.3 Treatment Assignment

In this prospective, single center, open-label, non-randomized, dose-escalation, comparative, safety study, Cohort 1 subjects will receive an IV administration of 100 μ g/ 5 mCi Tc 99m tilmanocept. Cohort 2 subjects will receive an IV administration of 100 μ g/ 10 mCi Tc 99m tilmanocept. Cohort 3 subjects will receive a SC and an IV administration of 200 μ g/ 5 mCi Tc 99m tilmanocept approximately one week apart. Cohort 1 will be the starting dose group. Four subjects will be enrolled into Cohort 1.

If one of the four Cohort 1 subjects experiences a noxious pharmacologic activity/an ADR, two more subjects will be treated at the same tilmanocept mass dose and same radiolabel level as the subject with the ADR. If 2 out of 4 or 3 out of 6 subjects experiences a noxious pharmacologic activity/an ADR in

Cohort 1, the maximum tolerated dose (MTD) cannot be determined. If no additional noxious pharmacologic activities/ADRs are observed in the expanded cohort, the dose escalation will continue with Cohort 2. If one additional noxious pharmacologic activity/ADR is observed, the current dose will be deemed the MTD. If more than one additional pharmacologic activity or ADR is observed in the expanded cohort, the previous dose will be deemed the MTD.

If no noxious pharmacologic activities/ADRs are experienced in Cohort 1, Cohort 2 will be open for enrollment.

Dose escalation will continue until the MTD is found or until Cohort 3 is reached with only one ADR or without any ADRs. The maximum tolerated dose is defined as the highest dose level at which no more than 33% of subjects experienced an ADR. Visual representation of the dose escalation scheme may be found in Appendix 2.

NOTE: Adverse Drug Reaction

An Adverse Drug Reaction (ADR) includes all noxious and unintended responses to a medicinal product related to any dose or dose regimen. The phrase “responses to a medicinal product” means that a casual relationship between a medicinal product and an adverse event is at least a reasonable possibility, i.e. the relationship cannot be ruled out.

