	
administration of 200 µg/ 5 mCi Tc 99m tilmanocept approximately one week apart. At least one subject enrolled into each cohort must meet inclusion criteria 4c, as defined above (suspected non-cutaneous or confirmed non-cutaneous KS). For determination of the primary endpoint, a review meeting for safety will be held after the completion of each cohort prior to opening the next dose cohort. Cohorts will be dosed per the following table:
 

	Tc 99m tilmanocept Dose	Route of Administration	Number of Subjects	

Cohort 1	100 µg/ 5 mCi	IV	n = 4	

Cohort 2	100 µg/ 10 mCi	IV	n = 4	

Cohort 3	200 µg/ 5 mCi	IV and SC	n = up to 6	

 
Following IV administration, all subjects will have a whole body planar scan with optional SPECT/CT region of interest scanning beginning at 60-75 minutes post-injection. Subjects in Cohort 3 will additionally have a whole body planar scan with optional SPECT/CT region of interest scanning beginning at 60-75 minutes and 4-6 hours following SC injection.
		Tc 99m tilmanocept Dose	Route of Administration	Number of Subjects	Cohort 1	100 µg/ 5 mCi	IV	n = 4	Cohort 2	100 µg/ 10 mCi	IV	n = 4	Cohort 3	200 µg/ 5 mCi	IV and SC	n = up to 6
	Tc 99m tilmanocept Dose	Route of Administration	Number of Subjects														
Cohort 1	100 µg/ 5 mCi	IV	n = 4														
Cohort 2	100 µg/ 10 mCi	IV	n = 4														
Cohort 3	200 µg/ 5 mCi	IV and SC	n = up to 6														

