Maximum TEAE Severity Grade				
Mild	xxx (xxx%)	xxx (xxx%)	xxx (xxx%)	xxx (xxx%)
Moderate	xxx (xxx%)	xxx (xxx%)	xxx (xxx%)	xxx (xxx%)
Severe	xxx (xxx%)	xxx (xxx%)	xxx (xxx%)	xxx (xxx%)
Highest Relationship of TEAE to Tc 99m Tilmanocept				
Definitely Not [n(%)]	xxx (xxx%)	xxx (xxx%)	xxx (xxx%)	xxx (xxx%)
Probably Not [n(%)]	xxx (xxx%)	xxx (xxx%)	xxx (xxx%)	xxx (xxx%)
Possibly [n(%)]	xxx (xxx%)	xxx (xxx%)	xxx (xxx%)	xxx (xxx%)
Probably [n(%)]	xxx (xxx%)	xxx (xxx%)	xxx (xxx%)	xxx (xxx%)
Definitely [n(%)]	xxx (xxx%)	xxx (xxx%)	xxx (xxx%)	xxx (xxx%)
Highest Relationship of TEAE to Study Procedure				
Definitely Not [n(%)]	xxx (xxx%)	xxx (xxx%)	xxx (xxx%)	xxx (xxx%)
Probably Not [n(%)]	xxx (xxx%)	xxx (xxx%)	xxx (xxx%)	xxx (xxx%)
Possibly [n(%)]	xxx (xxx%)	xxx (xxx%)	xxx (xxx%)	xxx (xxx%)
Probably [n(%)]	xxx (xxx%)	xxx (xxx%)	xxx (xxx%)	xxx (xxx%)
Definitely [n(%)]	xxx (xxx%)	xxx (xxx%)	xxx (xxx%)	xxx (xxx%)
Subjects with at Least One Serious TEAE Adverse Event	xxx (xxx%)	xxx (xxx%)	xxx (xxx%)	xxx (xxx%)

Cohort 1 = 100 μ g/5mCi IV; Cohort 2 = 100 μ g/10mCi IV; Cohort 3 = 200 μ g/5mCi IV and SC.
 STATKING Clinical Services (DD-MMM-YYYY)
 Source Program: xxxxxxxx.sas

Table 20. Number and Percent of Subjects with Adverse Drug Reactions
 Navidea Biopharmaceuticals - Study No. NAV3-24
 Safety Population (N=xxx)

Adverse Event Category ^a :	Cohort 1 (N=xxx)	Cohort 2 (N=xxx)	Cohort 3 (N=xxx)	Overall (N=xxx)
Total Number of Adverse Drug Reactions ^b	xxx	xxx	xxx	xxx
Subjects with at Least One Adverse Drug Reaction	xxx (xxx%)	xxx (xxx%)	xxx (xxx%)	xxx (xxx%)
System Organ Class 1	xxx (xxx%)	xxx (xxx%)	xxx (xxx%)	xxx (xxx%)
Preferred Term 1	xxx (xxx%)	xxx (xxx%)	xxx (xxx%)	xxx (xxx%)
Preferred Term 2	xxx (xxx%)	xxx (xxx%)	xxx (xxx%)	xxx (xxx%)
System Organ Class 2	xxx (xxx%)	xxx (xxx%)	xxx (xxx%)	xxx (xxx%)
Preferred Term 1	xxx (xxx%)	xxx (xxx%)	xxx (xxx%)	xxx (xxx%)
Preferred Term 2	xxx (xxx%)	xxx (xxx%)	xxx (xxx%)	xxx (xxx%)

^a Adverse events coded with MedDRA Coding Dictionary Version XXX.

^b Adverse drug reactions are defined as all noxious and unintended responses to a medicinal product related to any dose or dose regimen. The phrase 'responses to a medicinal product' means that a causal relationship between a medicinal product and an adverse event is at least a reasonable possibility, i.e. the relationship cannot be ruled out.

Cohort 1 = 100µg/5mCi IV; Cohort 2 = 100µg/10mCi IV; Cohort 3 = 200µg/5mCi IV and SC.

STATKING Clinical Services (DD-MMM-YYYY)

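### After cohort expansion, Protocol Section 5.3 counts ADRs where its other rules count subjects; in rare cases this changes which dose is named the MTD (minor)

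*Protocol*

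**What the plan says.** Section 5.3 of the protocol holds the whole escalation rule; the SAP restates neither an escalation rule nor an MTD rule. The section uses two counting units.

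**Subjects.** Expansion by two is triggered when one of the four Cohort 1 subjects has an ADR. The limit at which no MTD can be determined in Cohort 1 begins "If 2 out of 4 or 3 out of 6 subjects experiences a noxious pharmacologic activity/an ADR". The definition reads "The maximum tolerated dose is defined as the highest dose level at which no more than 33% of subjects experienced an ADR".

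**ADRs.** Three sentences apply after expansion. The first lets escalation go on to Cohort 2 when there are no further ADRs. The second makes the dose under test the MTD when there is a single further ADR. The third covers any larger number: "If more than one additional pharmacologic activity or ADR is observed in the expanded cohort, the previous dose will be deemed the MTD".

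The sentence that ends escalation is also worded in ADRs: Cohort 3 must be reached with one ADR at most.

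Elsewhere the unit is the subject. Section 9.2 makes the primary variable the presence or absence of an ADR in each subject, and SAP Section 5.0 uses the proportion of patients with at least one. SAP Table 20 (Appendix B) has one row for "Total Number of Adverse Drug Reactions" and another for "Subjects with at Least One Adverse Drug Reaction", so the plan treats events and affected subjects as different counts.

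**The concern.** Section 9 gives finding the MTD as a statistical objective, and these sentences are its decision rule. A subject can have more than one ADR. The definition has no severity threshold, and under Section 8.6.1.2 an event judged possibly related counts as related. Cohort 3 subjects also receive two injections, so one person could react to each. Section 5.3 does not say that several ADRs in one subject count once.

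Read literally, the post-expansion sentences can therefore name a different MTD from the one given by the subject-based definition in the same section. In Cohort 1 they can point to a previous dose that does not exist. The stake is the correctness of the MTD label.

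**Working it through.** **Plan's own figure.** Planned enrolment is 4 + 4 + up to 6 = up to 14, as Section 9.4 states. The design has no alpha, power or effect size to reproduce.

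**The two counts side by side.** Start from one affected subject among the first four, then add two subjects.

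| ADRs in the two added subjects | Later ADR in the original subject | Literal count of additional ADRs | Subjects affected |
|---|---|---|---|
| 0, 0 | no | 0: escalate | 1/6 = 16.7%: escalate |
| 1, 0 | no | 1: current dose is MTD | 2/6 = 33.3%: current dose is MTD |
| 2, 0 | no | 2: previous dose is MTD | 2/6 = 33.3%: current dose is MTD |
| 1, 1 | no | 2: previous dose is MTD | 3/6 = 50%: previous dose is MTD (Cohort 1: not determinable) |
| 0, 0 | yes, if counted as additional | 1: current dose is MTD | 1/6 = 16.7%: escalate |

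The counts lead to different decisions in rows three and five.

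- Row three: escalation stops under both counts and only the label differs. In Cohort 1 the literal result has no meaning: there is no lower dose, and the clause for an undeterminable MTD needs 3 of 6 subjects.
- Row five: escalation would stop wrongly, but only if a further ADR in a subject already counted is taken as additional.

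**Probabilities.** The documents give neither input, so both are assumptions: p is the chance that a subject has at least one ADR, and m (0.1 to 0.5) is the chance that an affected subject has several. Subjects are taken as independent.

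- Row three: P(1 of 4) × P(1 of 2) × m = 4p(1−p)³ × 2p(1−p) × m = 8p²(1−p)⁴m.
- Row five, upper limit: P(1 of 4) × P(0 of 2) × m = 4p(1−p)³ × (1−p)² × m = 4p(1−p)⁵m. This is a ceiling because it includes second ADRs seen before expansion, which are not additional on any reading.

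| p | 8p²(1−p)⁴ | Row three, m = 0.1 to 0.5 | 4p(1−p)⁵ | Row five ceiling, m = 0.1 to 0.5 |
|---|---|---|---|---|
| 0.01 | 0.00077 | 0.008% to 0.04% | 0.0380 | 0.4% to 1.9% |
| 0.05 | 0.0163 | 0.2% to 0.8% | 0.1548 | 1.5% to 7.7% |
| 0.10 | 0.0525 | 0.5% to 2.6% | 0.2362 | 2.4% to 11.8% |
| 0.20 | 0.1311 | 1.3% to 6.6% | 0.2621 | 2.6% to 13.1% |

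These are per 4+2 cohort. The expansion trigger is written out for Cohort 1 only, so applying it to later cohorts is a further assumption.

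**Which p is plausible.** Section 1.3.4 reports no drug-related reaction in 60 IV subjects with other indications. The one-sided 95% upper bound is 1 − 0.05^(1/60) = 4.9%, so for IV dosing the first two rows are the relevant ones. The SC pilot in KS (Section 1.2.1) had five subjects and two events, fatigue and nausea, judged possibly related to drug or procedures. That is 1 or 2 of 5 subjects, with exact 95% intervals of 0.5% to 71.6% and 5.3% to 85.3%, too wide to fix p.

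**End of escalation.** If one Cohort 3 subject has an ADR after each injection and no one else is affected, there are two ADRs but one affected subject. The literal end condition is not met, although the subject-based limit is.

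**The 33% limit.** 2/6 = 0.3333, which is greater than 0.33. By the definition a dose with 2 of 6 affected is not the MTD; by the one-additional rule it is. This conflict remains even when subjects are counted throughout.

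**The case against.** The strongest reply is that nobody would misapply the rule. Section 9.2 uses a yes/no variable per subject. The 3-of-6 limit stands directly before the disputed sentences, and 1 + 1 = 2 of 6 and 1 + 2 = 3 of 6 fit it exactly. A literal result that names a nonexistent dose is itself a reason to reject that reading. The Synopsis also ties the between-cohort review to the subject-based endpoint: "For determination of the primary endpoint, a review meeting for safety will be held after the completion of each cohort". Additional events in an expanded cohort naturally means those in the two added subjects, which removes row five. The dose escalation diagram could not be seen in the text available and may state the rule by subject.

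The reply also has the data on its side. Section 9.4 expects no ADRs, and Section 8.6.1.4 reports none in about 20 SC and 60 IV administrations beyond lymphatic mapping. A reader might infer from the pilot that two ADRs in one subject have already been seen. The text does not support that: three AEs in two subjects means one subject had two AEs, but one of the three was edema judged probably not related, and the text does not say who had which event.

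Nearly all of this stands and sets the size of the point. It does not remove the inconsistency. Section 9.2 defines an endpoint, not the escalation step, and Section 3.3 asks for strict adherence to the protocol as written. If the diagram counts subjects, the text of Section 5.3 still has to match it.

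**Conclusion.** The inconsistency is real, minor and unlikely to matter. Within one section the MTD decision rule changes its unit from subjects to ADRs. On the clear route (one added subject with several ADRs) the effect is limited to the MTD label. At an ADR risk of 5% or less, consistent with the IV experience, its probability is at most about 0.8% per 4+2 cohort. This rests on the assumed m of 0.1 to 0.5, on independence between subjects, and on carrying the Cohort 1 expansion rule to later cohorts.

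Three stronger conclusions might be inferred, and the documents do not support them:

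- That escalation would be stopped wrongly and Cohort 3, the only source of the IV versus SC comparison, lost. This needs the less natural reading in which a second ADR in the original subject counts as additional.
- That subjects are put at risk. Where the literal count differs after expansion, it names a lower dose or stops earlier, so the error is toward less exposure.
- That the primary analysis is affected. It is defined per subject and does not change.

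The mismatch between 33% and 2 of 6 is certain as arithmetic but editorial in weight.

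**What to change.** Reword the post-expansion and end-of-escalation sentences of Section 5.3 in additional subjects with at least one ADR:

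- None (1 of 6): escalate if a higher cohort remains. In Cohort 3, escalation ends with that dose tolerated.
- One (2 of 6): the current dose is the MTD.
- Two (3 of 6): the previous dose is the MTD; in Cohort 1 the MTD cannot be determined.

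Add one sentence saying that several ADRs in one subject count once, including ADRs after both Cohort 3 injections. Write the MTD limit as no more than one third of subjects (2 of 6). Check that the dose escalation diagram agrees; it is headed Appendix 3, although Section 5.3 refers to Appendix 2.

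The cost is a few sentences. No new data are needed and planned enrolment does not change.
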